2.8.2 Deaths

For overall and for each age group, death (including both cardiovascular and non-CV deaths) during the treatment period and the primary cause of death will be summarized using frequencies and percentages.

A listing of all deaths and heart transplant will also be provided for the SAF.

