### **12.4 Analysis of the primary endpoint(s)**

The primary objective is to evaluate safety and tolerability of LCZ696 in eligible heart failure patients from PANORAMA-HF receiving open-label investigational drug.

The primary safety assessment will be based on adverse events, which will be analyzed using frequencies and percentages.

The following adverse events will be summarized by primary system organ class, preferred term, and maximum severity as appropriate, for each age group and for overall, using numbers and percentages of patients with at least one adverse event in the corresponding class.

- Any adverse event (treatment emergent or not)
- Any serious adverse event (treatment emergent or not)
- Treatment emergent adverse event (TEAE)
- Treatment emergent serious adverse event
- Treatment emergent adverse event of special interest, i.e. hyperkalemia, hypotension, angioedema, renal impairment
- TEAE leading to dose adjustment, temporary dose interruption, or permanent discontinuation (including death) of study treatment
- TEAE leading to permanent discontinuation (including death) of study treatment

For overall and for each age group, death during the treatment period and the primary cause of death will be summarized using frequencies and percentages.

For overall and for each age group, the vital signs and the laboratory evaluations will be summarized by visit.

Adverse events (including SAEs), laboratory assessments, vital signs, and duration of drug exposure are considered primary endpoints.

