2.1.1 General definitions

Study treatment is sacubitril/valsartan.

The date of first administration of study treatment is the day of the first dose of sacubitril/valsartan.

The date of last administration of study treatment is the day of the last non-zero dose of sacubitril/valsartan.

Study day is defined as actual date – date of first administration of study treatment + 1.

Baseline is defined as last non-missing value before starting treatment, where for the same parameter, central laboratory result takes precedence over local laboratory result; in general values are obtained at the baseline visit (501), with the exception of urinalysis and complete laboratory, which are obtained at the screening visit (500). In case these two visits happened on the same day, results from the central laboratory will be considered as baseline values. Note that per protocol, in the case that visit 500 and, if applicable visit 501, is scheduled within 14

days of the PANORAMA-HF End of Study visit (Visit 416), the assessment results from PANORAMA-HF End of Study visit can be used as screening/baseline.

The **study period** starts with the date of screening visit (500) and ends with the date of end-of-study (EOS) or premature study discontinuation (PSD) visit (599).

Treatment period starts with the date when the first dose of study treatment is given (visit 501, unless no dose is given at that visit) and ends with the date of treatment disposition. In the case that no EOS visit was undertaken (e.g., because the patient died or withdrew from the study without such a visit), the treatment period ends with the death/withdrawal date or the last dose taken as reported in the DAR page. Subjects who permanently discontinued study drug should be scheduled for the discontinuation study Visit 599. Note that after a consecutive 3-month interruption of study treatment, subject should be discontinued from the study and should be seen at the site for Visit 599.

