2.8.1 Adverse events (AEs)

All AEs will be identified using Medical Dictionary for Regulatory Activities (MedDRA). The MedDRA version used for reporting the study will be described in a footnote.

An AE with its severity increased should be considered and recorded as a new AE.

Treatment emergent adverse events (TEAEs) are defined as any recorded AE with its start date-time (recorded or imputed) on or after the start date-time of the treatment period and end date as the end date of the treatment period or the date of last dose taken as reported in the DAR page + 30 days. Any AE happening after treatment discontinuation +30 days but still within the study period (e.g., where patient did not discontinue the study on the same date of treatment discontinuation) would not be considered as a TEAE and will be reported in the listing of AE.

The following adverse events will be summarized by primary system organ class, preferred term, and maximum severity as appropriate, for each age group and for overall, using numbers and percentages of patients with at least one adverse event in the corresponding class (see list below). Outputs will be produced for AEs regardless of study-drug relationship, and for study-drug related AEs. Study drug related AEs are defined as any recorded AE with “Reasonable possibility that AE is related to study treatment” answered as “YES”. Serious adverse events (SAEs) are defined as any recorded AE with “Does AE meet the definition of an SAE” answered as “Yes”.

Adverse events summaries

- Any adverse event (treatment emergent or not)
- Any serious adverse event (treatment emergent or not)
- Treatment emergent adverse event (TEAE)
- Treatment emergent serious adverse event
- Treatment emergent adverse event (TEAE) occurred in >5% of patients
- Treatment emergent serious adverse event (TESAE) occurred in >5% of patients

- Treatment emergent adverse event of special interest, e.g. angioedema (both, adjudicated and non-adjudicated), change in bone growth and density, cognitive impairment (narrow SMQ), embryo-fetal toxicity or lethality, hepatotoxicity, hyperkalemia, hypersensitivity, hypotension, malignancy, neonatal or infantile toxicity through exposure from breast milk, renal impairment (narrow SMQ), and/or statin drug interaction as defined in the Case Retrieval Sheet for LCZ696 (see [Section 2.8.1.1](#))

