- TEAE and TESAE leading to dose adjustment, temporary dose interruption, or permanent discontinuation (including death) of study treatment
- TEAE and TESAE leading to permanent discontinuation (including death) of study treatment
- TEAE and TESAE leading to death

The following rules are applicable to the summaries:

- If a patient reported more than one AE with the same PT, the patient will be counted only once with the greatest severity at the PT level
- If a patient reported more than one AE within the same SOC, the patient will be counted only once with the greatest severity at the SOC level, where applicable.

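### The death and cause-of-death table stops at treatment disposition, 30 days short of the fatal-TEAE window, and its end date is ambiguous when there is no end-of-study visit

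*SAP*

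**What the plan says.** **Death table.** SAP 2.8.2 summarises "death (including both cardiovascular and non-CV deaths) during the treatment period" and the primary cause, overall and for each age group. Protocol 12.4 has the same scope: "death during the treatment period and the primary cause of death will be summarized using frequencies and percentages". SAP 2.8.2 also promises a listing of all deaths and heart transplants in the Safety Set.

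**End of the treatment period.** Under SAP 2.1.1 the period "ends with the date of treatment disposition". If there was no end-of-study visit, for which the SAP gives the patient's death as an example, "the treatment period ends with the death/withdrawal date or the last dose taken as reported in the DAR page". No order of priority is given.

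**Fatal adverse events.** SAP 2.8.1 has a separate summary, "TEAE and TESAE leading to death". The TEAE definition names as its end either the end of the treatment period or "the date of last dose taken as reported in the DAR page + 30 days". The next sentence takes events out of the TEAE count only beyond the longer limit: "Any AE happening after treatment discontinuation +30 days but still within the study period". I therefore read the window as last dose + 30 days. A further summary, "Any serious adverse event (treatment emergent or not"), has no such limit.

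**The concern.** Long-term safety and tolerability is the only objective of this study, and the protocol's background describes paediatric heart failure as carrying significant mortality. The death and primary-cause table is the one most readers will take as the mortality result. Two features of its window cause trouble.

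- It has no days after treatment, although the fatal-TEAE table has 30 and the laboratory summaries (SAP 2.8.3) have 5. The report can carry two death counts that differ for reasons a reader cannot see from the tables.
- Whether a death is tabulated can depend on whether Visit 599 took place, which has nothing to do with drug or disease. Two programmers following SAP 2.1.1 could also reach different counts from the same data.

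At stake are the number of deaths and the distribution of causes in that table. No test, error rate or sample size is affected.

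**Working it through.** The plan states no death count or rate, so there is no figure to reproduce. The check sets the window rules side by side and runs typical cases through them.

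**Inputs**

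- Death table: treatment period only (SAP 2.8.2; protocol 12.4).
- Treatment period: to treatment disposition; with no end-of-study visit, to death/withdrawal or last dose (SAP 2.1.1).
- Fatal TEAEs: to last dose + 30 days, judged on the timing of the adverse event and not on the date of death (SAP 2.8.1).
- Permanent discontinuation means leaving the study and attending Visit 599 (protocol 6.5.1 and 9.1.1).
- Adverse events are followed for at least 30 days after last dose (protocol 10.1.1). SAEs are reported until 30 days after the last visit and, after that, only if the investigator suspects a causal relationship (protocol 10.1.3).

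**Cases**

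| Case | Death table | Fatal-TEAE table | Listing |
|---|---|---|---|
| A. Permanent stop, Visit 599 done, death on day 10 after last dose, event began within the window | No | Yes | Yes |
| B. As A, but no Visit 599 | Yes if the period ends at death; no if it ends at last dose | Yes | Yes |
| C. Drug temporarily held, not permanently stopped, then death with no end-of-study visit | Yes if the period ends at disposition or death; no if it ends at last dose | Yes if the event is in the window | Yes |
| D. Permanent stop, Visit 599 done, death later than last dose + 30 days | No | Only if the fatal event began within the window | Yes, if the death is known |

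A and B differ only in whether a visit was made, yet can be classified differently. B and C show that the unranked fallback matters in its own right. A patient who dies on treatment will have no end-of-study visit, so the fallback governs these deaths too. On the last-dose reading, even a death on the day after the final dose would fall outside the table.

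**Are the data available?** Yes, for the 30 days. The follow-up rules above cover last dose + 30 days.

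**Scale.** Change in the tabulated percentage = omitted deaths / N. Assume N = 173, the enrolment at 31-Jul-2021 given in the Amendment 1 rationale; this is not the final Safety Set.

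- One omitted death: 1/173 = 0.58 percentage points.
- Five omitted deaths: 5/173 = 2.9 percentage points.

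The range of one to five is an assumption. A larger final Safety Set would make each death count for less. Within an age group the denominator is smaller and each death counts for more, but the documents give no split.

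**The case against.** The best defence is that nothing is lost. Every death in the Safety Set is listed. The patient in case A also appears, with a number and percentage by age group and overall, in the fatal-TEAE table, and the event falls within the all-SAE summary. The death table is labelled as a treatment-period count, follows protocol 12.4, and does not claim to be total mortality. One table classifies by date of death and the other by timing of the adverse event, so some difference between them is expected. The study is single-arm and descriptive. The gap is also limited: drug held temporarily does not by itself end the treatment period under the general rule, and where death prevents a final visit the SAP allows the period to run to death.

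Most of that stands, and it rules out two stronger readings that a reader might draw. One is that deaths are concealed or that the study's mortality is shown to be biased low. The documents do not support this, given the listing, the fatal-TEAE table and the explicit label. What can be said is that any omission can only lower this one table's count. The other is that drug is often stopped because the patient is dying, so that the omissions are informative. Neither document says how often that happens.

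The defence does not remove the core. The fatal-TEAE table is arranged by system organ class and preferred term and keyed to adverse-event timing, so it does not replace a count of deaths by primary cause. A listing gives no frequencies. The end date without an end-of-study visit remains undefined.

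**Conclusion.** The point holds as a reporting inconsistency that should be corrected. As written, the death and primary-cause table omits a patient who permanently stops drug, completes Visit 599 and dies within 30 days, and it may include the same death had the visit been missed. The SAP does not depart from the protocol here; both use the same short window.

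The size is unknown, because the documents give no number of affected deaths. At the assumed N = 173, each one is about 0.58 percentage points. The conclusion rests on reading the TEAE window as last dose + 30 days, which the SAP's own follow-on sentence supports, and on treatment disposition being recorded no later than Visit 599 in a patient who stops permanently. It does not extend to a claim that total mortality would be misreported.

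**What to change.** 1. In SAP 2.8.2, keep the treatment-period row and add a row for deaths and primary cause from first dose to last dose + 30 days, by age group and overall.
2. In SAP 2.1.1, state which end date applies when there is no end-of-study visit, so that each death has one classification.
3. Leave deaths known only later in the listing, or show them as a count with a footnote that ascertainment is incomplete beyond 30 days after the last visit. A percentage over all known follow-up would mix complete reporting with reports selected on suspected causality, and is better avoided.

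The cost is a row or two in one table and one sentence of definition, using data already collected. The tabulated death count may rise. The two tables need not agree exactly even then, since one goes by date of death and the other by adverse-event timing; a short footnote should say so.

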2.8.3 Laboratory data

Complete and abbreviated laboratory evaluations are described in [Table 2-2](#). Complete laboratory evaluations (hematology, blood chemistry, and urine) are performed at screening (Visit 500), and subsequently every 12 months from Visit 501 until End of Study (Visit 599); these analyses are performed at central laboratory.

Abbreviated safety laboratory evaluation consists of serum sodium, potassium, creatinine, and eGFR. Abbreviated laboratory evaluations are performed every 12 months starting from visit at 6 months (Visit 507). In addition, abbreviated laboratory assessments are performed at up-titration visits (visits 501, 502, 503, 504 and 505, as applicable), and unscheduled visits with planned dose level changes; these analyses can be performed at central or local laboratories. Laboratory data will be reported for the treatment period. Note that a window of 5-day will be used to include laboratory data performed within 5 days after the discontinuation of treatment.

Table 2-4 Laboratory Assessments

Hematology	Biochemistry	Urine measurements**
Hematocrit	Alanine aminotransferase (ALT)	Specific gravity
Hemoglobin	Albumin (Alb)	pH
Platelet count	Alkaline phosphatase (ALP)	Glucose
Red blood cell count (RBC)	Aspartate aminotransferase (AST)	Protein (Total)
White blood cell count (WB)	Blood urea nitrogen (BUN)	Ketones
WBC differential	Calcium	Bilirubin
	Magnesium	Urobilinogen
	Phosphate	Hemoglobin (blood)
Red blood cell distribution width (RDW)	Chloride	Leukocyte esterase
Mean corpuscular volume (MCV)	Creatinine*	Nitrite
Mean corpuscular hemoglobin concentration (MCHC)	Glucose	WBC
	Potassium	RBC sediments
	Sodium	Hyaline casts
	Bicarbonate	Granular casts
	Total bilirubin (TBL)	Waxy casts
	Fractionated bilirubin (if total bilirubin > 2x ULN)	WBC casts
	Total protein	RBC casts
	Uric acid	
	eGFR*	

*Abbreviated laboratory evaluations must include these parameters

**Urinalysis with dipstick includes specific gravity, pH, glucose, total protein, bilirubin, ketones, urobilinogen, nitrite, leukocytes esterase and hemoglobin (blood). Other urine measurements listed are not required. If a urine dipstick is positive, other urine measurements such as a qualitative microscopic determination of WBC, RBC sediments (and casts) should also be measured.

Both complete laboratory evaluations and abbreviated laboratory evaluations will be included in the summaries for laboratory data. In general, local lab and central lab data will be analyzed separately. However, for shift tables, where only abnormal/normal values are used, they may be summarized together. Here, “summarized together” means the following:

- 1) For each patient, the shift will be calculated either within local lab, or within central lab.
- 2) In the shift table, these shifts will be presented together. If shifts within both, local lab and central lab are available, at the same visit, only shifts within the central lab will be shown.

Test values and change from baseline based on the local laboratory assessments and the central laboratory assessments will be summarized by laboratory parameter, age group (and overall) and visit, using number of observations, mean, standard deviation, median, minimum, Q1, Q3, and maximum.

The shift from baseline will be summarized by laboratory parameter, age group and visit, using the numbers and percentages of patients in each category (low/normal/high).

For missing lab data at a given visit (except for lab performed after IMP discontinuation), the missing data will be taken from an unscheduled visit between two scheduled visits if they are available. Otherwise will leave them as missing. The data from the unscheduled visit for the missing data imputation will use the central lab data for tables reporting central lab analyses, and local lab data for table reporting local lab analyses.

Clinically notable laboratory abnormality

[Table 2-3](#) provides criteria for clinically notable laboratory abnormalities.

The clinically notable laboratory abnormalities during the treatment period based on the local laboratory assessments and the central laboratory assessments will be summarized together (the definition of “summarized together” is the same as that for the shift tables described above) by criteria and age group, using the numbers and percentages of patients satisfying such criteria.

Table 2-5 Clinical notable criteria for laboratory values

Parameter	Conventional Units	SI Alert Value	SI Units
Hematology			
Red Blood Cell Count	x10E6/uL	>50% increase and >ULN; >30% decrease and <LLN.	x10E12/L
Hemoglobin	g/dL	>50% increase and >ULN; (>30% decrease and <LLN) or any value <70.	g/L
Hematocrit	%	>50% increase and >ULN; >30% decrease and <LLN.	L/L
White Blood Cell Count	x10E3/uL	>50% increase and >ULN; >50% decrease and <LLN.	x10E9/L
Platelet Count	x10E3/uL	>75% increase and >ULN; >50% decrease and <LLN.	x10E9/L
Chemistry			

BUN	mg/dL	>50% increase and >ULN	mmol/L
Creatinine	mg/dL	>50% increase and >ULN	umol/L
Albumin	g/dL	<20	g/L
Glucose	mg/dL	>50% increase and >ULN; (>50% decrease and <LLN) or any value <3.3.	mmol/L
Total Bilirubin	mg/dL	>100% increase and >ULN	umol/L
AST (SGOT)	U/L	>150% increase and >ULN	U/L
ALT (SGPT)	U/L	>150% increase and >ULN	U/L
Sodium	mEq/L	(>5% increase and >ULN) or any value >150; (>5% decrease and <LLN) or any value <125	mmol/L
Potassium	mEq/L	(>20% increase and >ULN) or any value >6; (>20% decrease and <LLN) or any value <3.	mmol/L
Chloride	mEq/L	>10% increase and >ULN; >10% decrease and <LLN	mmol/L
Calcium	mg/dL	>10% increase and >ULN; >10% decrease and <LLN.	mmol/L
Uric Acid	mg/dL	>50% increase and >ULN	mmol/L

Liver events

[Table 2-4](#) provides criteria for liver laboratory triggers and liver events.

The liver laboratory triggers and liver events during the treatment period based on the local laboratory assessments and the central laboratory assessments will be summarized together by criteria and age group, using the numbers and percentages of patients satisfying such criteria.

Table 2-6 Liver event and laboratory trigger definitions

Definition / threshold	
LIVER LABORATORY TRIGGERS	
 • $3 \times \text{ULN} < \text{ALT} / \text{AST} \leq 5 \times \text{ULN}$ • $1.5 \times \text{ULN} < \text{TBL} \leq 2 \times \text{ULN}$
LIVER EVENTS	
 • ALT or AST $> 5 \times \text{ULN}$ • ALP $> 2 \times \text{ULN}$ (in the absence of known bone pathology) • TBL $> 2 \times \text{ULN}$ (in the absence of known Gilbert syndrome) • ALT or AST $> 3 \times \text{ULN}$ and INR > 1.5 • Potential Hy's Law cases (defined as ALT or AST $> 3 \times \text{ULN}$ and TBL $> 2 \times \text{ULN}$ [mainly conjugated fraction] without notable increase in ALP to $> 2 \times \text{ULN}$) • Any clinical event of jaundice (or equivalent term) • ALT or AST $> 3 \times \text{ULN}$ accompanied by (general) malaise, fatigue, abdominal pain, nausea, or vomiting, or rash with eosinophilia • Any adverse event potentially indicative of a liver toxicity*

Definition / threshold

*These events cover the following: hepatic failure, fibrosis and cirrhosis, and other liver damage related conditions; the non-infectious hepatitis; the benign, malignant and unspecified liver neoplasms

TBL: total bilirubin; ULN: upper limit of normal

Renal events

Renal events are defined using the following two categories of criteria.

1. Serum event:

- a. Serum estimated GFR* decrease $\geq 25\%$ compared to baseline AND eGFR $< 90 \text{ mL/min}/1.73\text{m}^2$
- b. Serum estimated GFR* decrease $\geq 50\%$ compared to baseline

Note that *eGFR is calculated using a modified Schwartz formula for patients <18 years:

$\text{eGFR} (\text{ml/min}/1.73\text{m}^2) = 0.413 \times \text{height (cm)} / \text{serum creatinine (mg/dl)}$.

2. Urine event:

- a. New onset ($\geq 1+$) proteinuria
- b. New onset ($\geq 1+$) hematuria
- c. New onset ($\geq 1+$) glucosuria

The renal events during the treatment period based on the local laboratory assessments and the central laboratory assessments will be summarized together by criteria and age group (and overall), using the numbers and percentages of patients satisfying such criteria.

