## **6.5 Dose escalation and dose modification**

### **6.5.1 Dose modifications**

The study drug is up titrated every 2 weeks as tolerated to target dose (dose level 4) as outlined in [Table 3-2](#) and based on the safety monitoring criteria ([Table 3-1](#)). Following up titration, the maximum tolerated or target dose will then be maintained for the duration of the study. Both scheduled and unscheduled visits can be utilized for up-titration and/or down-titration throughout the study based on investigator judgment.

For subjects who are unable to tolerate the protocol-specified dosing scheme, dose level adjustments and temporary interruptions of less than 3 months of study treatment are permitted. The following guidelines should be followed:

- The investigator should adjust/interrupt/discontinue doses of concomitant medications if it is believed that they are the most likely cause of an adverse event.

- If adjustment/elimination of concomitant medications is not possible or does not alleviate the adverse event of concern, the investigator may down titrate to the next lower study drug dose level ([Table 3-2](#)) to temporary or permanent discontinuation of study drug.
- The subject may reinitiate the higher dose when the investigator feels it is appropriate to do so per the directions provided below in this section.
- If the study drug is permanently discontinued, the subject should be discontinued from the study (Visit 599).

Subjects may be seen at any time for unscheduled visits during the study for re-evaluation of safety criteria parameters. Study drug dose level adjustments should mainly be based on overall safety and tolerability with focus on a) hyperkalemia, b) symptomatic hypotension and c) renal dysfunction. Laboratory assessments of serum sodium, potassium, creatinine, and eGFR (calculated based on the modified Schwartz formula ([Schwartz and Work 2009](#)) will be utilized. Refer to [Appendix 4](#), [Appendix 6](#), and [Appendix 7](#) for treatment guidelines for renal dysfunction, management of hypotension and hyperkalemia, respectively.

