### **Study drug restart after temporary treatment interruption**

Subjects who have temporarily discontinued study drug should be restarted as soon as possible as deemed appropriate by the investigator. The investigator should restart the subject on the study drug at the most appropriate dose level ([Table 3-2](#)) as per the investigator's clinical judgment. If the subject does not tolerate the newly restarted study-drug dose level, they may be down titrated again (if appropriate) or the study medication may be temporarily discontinued again.

Subjects restarted on the study drug will retain their original study identification numbers.

Investigators may discontinue a subject's study drug due to serious or intolerable AEs suspected to be causally related to study drug. If study drug is discontinued for any reason, this must be recorded on the DAR eCRFs. In addition, subjects who permanently discontinued study drug should be scheduled for the discontinuation study Visit 599.

If during study treatment interruption a subject requires treatment with an ACEI a  $\geq 36$  hours washout should be observed before the ACEI is initiated. The ACEI must be discontinued  $\geq 36$  hours prior to restarting study drug. Subjects who have temporarily discontinued study drug and are presently taking an ARB or a renin inhibitor must discontinue their current ARB or renin inhibitor on the day study drug is restarted.

Note that after a consecutive 3-month interruption of study treatment, subject should be discontinued from the study and should be seen at the site for Visit 599).

If the subject becomes pregnant during the course of the study, the subject has to discontinue study drug immediately and should be seen at the site for Visit 599 and evaluated for transition to alternative treatment per the Investigator's clinical judgement.

Refer to ([Section 8.4.2](#)) for further details on pregnancies and reporting guidelines.

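### The SAP drops labs more than 5 days after treatment discontinuation but counts labs from any point of a temporary interruption of up to about 3 months as on-treatment

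*SAP*

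**What the plan says.** **Treatment period.** SAP 2.1.1: "Treatment period starts with the date when the first dose of study treatment is given" "and ends with the date of treatment disposition" (the start and end of one definition). A related definition reads "The date of last administration of study treatment is the day of the last non-zero dose of sacubitril/valsartan". A zero-dose gap followed by a restart therefore does not end treatment.

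**Laboratory data.** SAP 2.8.3: "Laboratory data will be reported for the treatment period", followed by "Note that a window of 5-day will be used to include laboratory data performed within 5 days after the discontinuation of treatment". The SAP revision history dates this window to August 2023, so it was a deliberate choice. The same section lets an unscheduled visit supply a missing scheduled lab value. The only exception is for labs done after the investigational product was discontinued.

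**Adverse events.** SAP 2.8.1 counts an event as treatment-emergent if it has its "start date-time (recorded or imputed) on or after the start date-time of the treatment period". The count closes at the end of the treatment period or 30 days after the last dose. Interruptions are not mentioned.

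**Interruptions.** Protocol 6.5.1: "dose level adjustments and temporary interruptions of less than 3 months of study treatment are permitted". No limit on their number is stated. Its restart subsection opens a washout rule with "If during study treatment interruption a subject requires treatment with an ACEI", and also covers children on an ARB or renin inhibitor at restart. Protocol 6.2.2 has study drug stopped temporarily when one of these drugs is needed.

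**What the SAP already derives.** SAP 2.4.1 defines no-treatment dosing intervals, counts patients with interruptions over 24 hours and over 14 days, and defines exposure both with and without interruptions. SAP 2.4.2 tabulates concomitant ACEI, ARB and renin-inhibitor use. No safety table is expressly linked to any of these.

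**The concern.** The 5-day limit implies that a lab value taken well after the last dose no longer describes a child on sacubitril/valsartan. The same reasoning applies to a value taken weeks into an interruption, yet no rule removes or marks it, even when another renin-angiotensin drug is being taken.

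Protocol 6.5.1 ties interruptions largely to tolerability, so some of these values will be recovering potassium, creatinine or blood pressure. In a by-visit mean or a shift table they sit among on-drug values and pull the summary toward normal. The fill rule adds a second route. Appendix 4 calls for creatinine at least weekly in its action situation, including when drug is stopped. Appendix 7 calls for repeat potassium within days when drug may be temporarily stopped. An unscheduled off-drug result can then stand in for a missed scheduled one.

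Safety is the only objective, there is one arm, and SAP 2.5.4 plans no supportive analyses. No other planned table would show the mixing.

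**Working it through.** There is no sample size, power or error rate to reproduce. The check applies the SAP's date rules to two cases and then sizes one gap.

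**Inputs**
- 1 month = 30.4375 days (SAP 2.4.1), so 3 months = 3 × 30.4375 = 91.3 days. A permitted gap is just under this.
- Lab tail 5 days (SAP 2.8.3); adverse-event tail 30 days (SAP 2.8.1).
- Follow-up of 1 to about 4.5 years (protocol section 3).
- Assumption for a permanent stop: the disposition date is the last-dose date.

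**Step 1. The same off-drug day under each rule**

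| Days since last dose | Lab, gap then restart | Lab, permanent stop | AE, gap then restart | AE, permanent stop |
|---|---|---|---|---|
| 3 | in | in | in | in |
| 6 | in | out | in | in |
| 20 | in | out | in | in |
| 45 | in | out | in | out |
| 85 | in | out | in | out |

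For labs the two cases part after day 5; for adverse events, only after day 30.

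**Step 2. Days treated differently in the longest gap**
- Labs: 91.3 − 5 = 86.3 days. The gap is 91.3 / 5 ≈ 18 times the window.
- Adverse events: 91.3 − 30 = 61.3 days.

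**Step 3. Scheduled labs that can fall in a gap**
After titration, site visits are 6 months apart (protocol section 8), or 182.6 days. A gap under 91.3 days holds at most one scheduled lab visit. With random timing, the chance that it holds one is at most 91.3 / 182.6 = 50%. During titration, visits are about 2 weeks apart, so a gap there can hold more.

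**Step 4. Which tables can move**
- By-visit lab means and changes, and shift tables: a recovered value can dilute these.
- By-visit vital signs: scheduled assessments only (SAP 2.8.4.2), so only a visit falling inside a gap matters.
- Potassium, eGFR and creatinine thresholds (SAP 2.8.1.1), notable labs and renal events (SAP 2.8.3): these count patients who ever met a criterion. A recovered value cannot remove a patient. A value taken on a substitute drug could add one.

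**Step 5. Rate denominator**
SAP 2.8.1.1 gives rates per 100 patient-years without saying which exposure duration is used. For one child with one longest gap, the rate including interruption time, relative to the rate excluding it, is (T − 91.3) / T:
- T = 1 year: (365.25 − 91.3) / 365.25 = 0.75
- T = 2 years: (730.5 − 91.3) / 730.5 = 0.875
- T = 4.5 years: (1643.6 − 91.3) / 1643.6 = 0.944

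A 14-day gap in 1 year gives (365.25 − 14) / 365.25 = 0.962.

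**The case against.** Counting adverse events through interruptions is a usual convention, and stopping and restarting is part of the protocol's regimen. A treatment-emergent event is a timing category, not an attribution. That stands, and the current event tables should stay.

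Three stronger readings are tempting, and the documents do not support them:
- **That events arising on a substitute ACEI or ARB are charged to the study drug.** SAP 2.8.1 also produces a separate set of outputs for drug-related events, from which an event the investigator judges unrelated drops out.
- **That tolerability will look better overall.** The ever-met tables cannot be diluted, so the direction is arguable only for by-visit means and shifts.
- **That a quarter of the data is off-drug.** The 25% (91.3 / 365.25) is one child's worst-case person-time in a 1-year stay, not a share of the values in any table.

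Two further limits stand. Unscheduled labs linked to dose changes are done locally (protocol 8.4.1), and the fill rule keeps central and local data apart, so filling a central-lab table needs an unscheduled central sample. The inclusion of off-drug labs is also inferred from definitions: SAP 2.8.3 does not say whether discontinuation means permanent only, and the protocol uses the word for temporary stops too. The permanent reading is the natural one, because the SAP has a separate term for interruptions, but it needs a sentence.

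**Conclusion.** The inconsistency is real for laboratory data. Labs are cut 5 days after a permanent stop and not at all during an interruption of up to about 91 days, and the fill rule can carry off-drug values into scheduled visits. By-visit means and shift tables are exposed; ever-met threshold tables are not open to dilution. For adverse events only onset beyond day 30 of a gap is treated differently, which is a minor point given normal practice. The rate denominator is unspecified rather than shown to be wrong.

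The size is unknown, because neither the number of interruptions nor the number of children given another renin-angiotensin drug is stated. Scheduled visits 6 months apart suggest that few scheduled values per child are affected after titration. The conclusion assumes that discontinuation in SAP 2.8.3 means permanent discontinuation and that disposition falls on the last-dose date. If disposition is later, off-drug labs up to that date are also included. This is a cheap improvement to a descriptive analysis, not a flaw that invalidates it.

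**What to change.** Keep every current table and add:
1. A flag for lab and vital-sign values taken more than 5 days into a no-treatment interval, with a supportive by-visit summary showing them separately. The SAP sets 5 days for labs only, so using it for vital signs is an extension to be stated.
2. A sentence in SAP 2.8.3 saying that the 5-day window refers to permanent discontinuation, and that flagged labs may not fill a missing scheduled visit.
3. A supportive on-drug table of special-interest events, using the SAP's own 30-day tail after the last dose before each interruption. Mark events with onset during ACEI, ARB or renin-inhibitor use.
4. The denominator of the exposure-adjusted rates in SAP 2.8.1.1. Use exposure excluding interruptions in the supportive table, with a footnote that the 30-day tail admits some events from days outside that denominator.

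The cost is one flag from existing dosing and concomitant-medication records, some SAP wording and a few supportive tables, with no new data collection. The on-drug summaries lean toward children who tolerate the drug, so they should supplement the main tables and not replace them. For the same reason, simply deleting interruption values from the main by-visit summaries is not advised.
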